**12. DIRECT ACCESS TO SOURCE DATA/DOCUMENTS**

Direct access will be granted to authorised representatives from the Sponsor, host institution and the regulatory authorities to permit trial-related monitoring, audits and inspections.

**13. QUALITY CONTROL AND QUALITY ASSURANCE PROCEDURE**

The study will be conducted in accordance with the current approved protocol, ICH GCP, relevant regulations and standard operating procedures.

The University of Leicester, as the study Sponsor, operates a risk based monitoring system to which this study will be subject.

## **14. CODES OF PRACTICE AND REGULATION**

### **14.1 Ethics**

All informed consent taken from MCI patients, VascD patients, AlzD patients and HC subjects will be taken following GCP guidelines.

JDR is funded by Department of Health working in partnership with the charities Alzheimer Scotland, Alzheimer's Research UK and Alzheimer's Society and is Health Research Authority (HRA) endorsed. The online service and all associated documentation, methods of contacting volunteers and handling of data, were reviewed by a specially convened HRA committee which included experts in research ethics, data protection and information governance. Formal endorsement was issued by the HRA in a letter dated 20 May 2014.

### **14.2 Sponsor Standard Operating Procedures**

All relevant Sponsor Standard Operating Procedures will be followed to ensure that this study complies with all relevant legislation and guidelines.

### **14.3 Declaration of Helsinki**

The investigator will ensure that this study is conducted in full conformity with the current revision of the Declaration of Helsinki (last amended October 2008).

### **14.4 ICH Guidelines for Good Clinical Practice**

The Investigator will ensure that this study is conducted in full conformity with relevant regulations and with the ICH Guidelines for GCP.

### **14.5 Approvals**

Once Sponsor authorisation has been confirmed, the protocol, informed consent form, participant information sheet and any proposed advertising material will be submitted to an appropriate Research Ethics Committee (REC), HRA, and host institution(s) for written approval.

Once Sponsor authorisation has been confirmed, the investigator will submit and, where necessary, obtain approval from the above parties for all substantial amendments to the original approved documents.

#### **14.6 Participant Confidentiality**

The trial staff will ensure that the participants' anonymity is maintained. The participants will be identified only by initials and a participant's ID number on the CRF and any electronic database. All documents will be stored securely and only accessible by trial staff and authorised personnel. The study will comply with the Data Protection Act, which requires data to be anonymised as soon as it is practical to do so.

## **15. DATA HANDLING AND RECORD KEEPING**

### **15.1 Data Extraction**

As supportive evidence of the diagnosis of MCI, VascD and AlzD, results and significant findings from Computerised Tomography (CT) head/Brain Magnetic Resonance Imaging (MRI), if undertaken, will be recorded on the CRF.

Other information which will be extracted from the medical notes and recorded on the CRF include results and details of any previous cognitive testing, and the date of diagnosis of MCI, VascD or AlzD.

### **15.2 Data Analysis**

All other parameters recorded, including CBFv, heart rate, BP, and ETCO2 will be simultaneously recorded onto a computer system (PHYSIDAS), providing data for subsequent analyses. Off-line analyses will be undertaken using software designed by the University of Leicester's Medical Physics Group.

### **15.3 Data Management**

All parameters (signals) that are collected during the measurement will be saved using a coded filename. The name and other identifying detail will NOT be included in any study data electronic file.

All files will be encrypted and stored on a password secured computer/laptop, which will have restricted access by members who are authorised on the authorisation log.

**16. STUDY GOVERNANCE**

The trial management group, which consists of the CI, co-applicants, and other research staff, will meet monthly to monitor study progress, and recruitment targets. As this is a prospective observational study and is not a therapeutic study, a data safety monitoring committee is not required.

## **17. FINANCING AND INSURANCE**

In this study, [name], [name] and [name] will supervise the researcher who is responsible for patient recruitment, data collection and analysis. [name] will take a lead role in preparing the experimental procedures. [name] will take responsibility for guiding patient recruitment. [name] will supervise data analysis, and [name] will also have a key role in the interpretation of results in terms of physiology and clinical relevance.

In this study, the extra assessments on patients will be carried out by the researcher, and all the equipment to be used is provided, serviced and maintained by the Department of Medical Physics, University of Leicester. No other patient related costs will be incurred by the project in addition to the routine care provided from the University Hospitals of Leicester NHS Trust or Leicestershire Partnership Trust.

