In addition to studying CBFv, NVC and VMR, by using transfer function analysis (TFA) further haemodynamic data can be obtained and calculated using TCD and beat-to-beat blood pressure monitoring. These data include coherence, phase, gain, autoregulatory index (ARI), critical closing pressure (CrCP) and resistance area product (RAP). By examining the transfer of BP fluctuations to CBF as a measure of CA, TFA makes it possible to examine the effect of changes in arterial blood pressure (BP) on CBFv. It quantifies the extent to which the input signal, BP, is reflected in the output signal, CBFv, and was first proposed by Giller in 1990. The parameter which tests the

linearity between the input and output signals at each frequency is called the coherence, with values of coherence ranging between zero and one. Values of coherence approaching one indicate a perfect linear relationship between input and output (i.e. CBFv and BP). Although there is currently no consensus on the threshold at which good coherence is assumed, many studies have adopted a coherence of  $\geq 0.5$  to accept the relationship as significant [Panerai et al 1998, Panerai et al 2006]. Phase is equivalent to the shift in radians from 0 to  $2\pi$  (or degrees from  $0^\circ$  to  $360^\circ$ ) that would be required to align input (BP) with output (CBFV) at a given frequency, and so gives an indication of the relative timing of the two signals. The magnitude of the phase response may be an indicator of the integrity of the autoregulatory response; phase is positive in intact CA (CBFv recovers faster than changes in BP) and it tends to zero in impaired CA when CBFv tends to follow BP, during steady-state conditions [Panerai et al 1998, Birch et al 1995]. Gain is the ratio of the amplitude of the output signal to the input signal, and so indicates the magnitude of change in CBFv that is due to a change in BP. Although gain alone is not a reliable measure of CA, an increase in gain suggests that CA is impaired, whereas a low gain indicates an efficient CA [Giller 1990, Van Beek et al 2008].

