### **6.2 Primary and Secondary Endpoints/Outcome Measures**

This is not an intervention study, and therefore it would not be appropriate to assess the classical primary and secondary outcome measures such as death and disability for this study. However, we intend to evaluate the following relevant outcomes:

- 1) The percentage of recruited subjects (HC, MCI patients, VascD patients and AlzD patients) able to comply with the full measurement protocol.
- 2) The percentage of measurements rejected because of aspects related to data quality during the analysis protocol, with recorded reasons.
- 3) Overall, the percentage of recruited subjects (healthy controls, MCI patients, VascD patients and AlzD patients) in whom values for the following parameters can be derived:
  - % change of CBFv at baseline in response to performance of the ACE-III Cognitive Examination
  - Autoregulation index (using the Tiecks model and from the phase, gain and coherence).

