to ensure they meet the study specific inclusion and exclusion criteria. Participants will only be referred to the researcher if the direct care team, based on the patient's cognitive functioning and clinical assessment determine that the patient will have capacity to consent to the study. Capacity will then be assessed formally by the researcher at the initial stage of information provision and at the formal consent process after a cooling off period of up to 7 days. These patients will be introduced to the researcher by the responsible clinical physician or specialist nurse for the provision of further study specific information, in the form of *Participant (Patient) Information Leaflet*. After provision of study specific information, the researcher will assess the patient's capacity in accordance with the Mental Capacity Act 2005. This is a 2 stage process where firstly, there must be a concern that the patient may lack capacity (in this case due to cognitive impairment). When the study information is provided to participants, it will be assessed in 4 steps. Firstly, the ability to understand the information, secondly to weigh up the information, thirdly to retain the information, and finally be able to communicate the decision back to the researcher. This initial discussion and assessment will take place at the outpatient memory clinic and stroke clinic at the LPT and UHL respectively, or through the participant's preferred contact method if recruiting from Join Dementia Research.

Age-, gender-, BP-matched HC will be recruited from University of Leicester departmental volunteers, patients' relatives and friends, and by poster advertisement (using *Research Participant Poster*) displayed in outpatient clinics at the University Hospital of Leicester (UHL) NHS Trust. Care will be taken to ensure that the HC are matched to the patients in terms of age, gender, and medical co-morbidities. HC will be provided with a volunteer specific information leaflet (*Participant (Volunteer) Information*).

After study specific information has been provided to the patients or volunteers, the researcher's contact details will be provided at the end of the PIS and the patient or volunteer will be able to contact the researcher directly if they wish to participate in the study.

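### The researcher who knows each diagnosis also records and analyses the signals; with no stated masking or acceptance rules, signal-derived group comparisons are open to assessor bias

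*Combined protocol and SAP*

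**What the plan says.** Section 17 puts three tasks with one supervised person: "the researcher who is responsible for patient recruitment, data collection and analysis". It adds that "the extra assessments on patients will be carried out by the researcher", and that another team member "will supervise data analysis".

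That person will know the group. Section 7.2 says of clinic patients: "These patients will be introduced to the researcher by the responsible clinical physician or specialist nurse". The researcher screens Join Dementia Research volunteers personally, against criteria that differ by group. Section 8.3 has the date of diagnosis taken from patients' records.

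Section 6.2 lists as an outcome "The percentage of measurements rejected because of aspects related to data quality during the analysis protocol, with recorded reasons". It also lists the percentage of participants in whom CBFv change and ARI can be derived.

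Section 15.3 says "All parameters (signals) that are collected during the measurement will be saved using a coded filename", in a passage about keeping identities out of the files. Section 15.2 says only that off-line analysis uses in-house software. The one signal-quality threshold mentioned, coherence of at least 0.5, appears in section 4 as the practice of other studies, after the remark that "there is currently no consensus on the threshold at which good coherence is assumed". Nothing in the protocol mentions masking, blinding or an independent reader.

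**The concern.** Signal acceptance comes before every CBFv and ARI value. If the person applying it knows the diagnosis and has no fixed rule, expectations about a group can influence which recordings survive, even without intent. The outcomes exposed are the CBFv comparison (primary objective), the ARI comparison (first secondary objective) and the section 6.2 percentages of rejected measurements and derivable parameters.

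There are many such decisions. Section 8.4 plans four recordings per participant with bilateral insonation, so 44 participants yield up to 44 × 4 × 2 = 352 velocity recordings at the first visit. With 11 analysable participants per group, losing a single selected value can move a group mean noticeably.

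**Working it through.** **Step 1: is the analyst masked anywhere?**

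- Tasks: recruitment, data collection and analysis sit with one researcher (section 17).
- Knowledge of group: introduction by the treating clinician, or the researcher's own screening (section 7.2).
- Rejection: takes place during analysis with reasons logged; no criteria and no named role (section 6.2).
- Acceptance rule: none in sections 8.4, 11.1 or 15.2; coherence appears only as background (section 4).
- Coding: filenames are coded (section 15.3), but nothing says that the code conceals group or that the analyst lacks the key.

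No statement separates knowledge of diagnosis from the acceptance decision.

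**Step 2: the plan's own figure.** Section 11.2 gives 11 per group for an ARI difference of 2 units, 80% power and 5% significance. It states no SD, test or sidedness, so 11 cannot be reproduced directly. Solving backwards with the two-sample normal formula:

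SD = Δ / [(z₁₋α/₂ + z₀.₈₀) × √(2/n)] = 2 / [(1.960 + 0.842) × √(2/11)] = 1.67

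Other assumptions give:

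- normal approximation, one-sided: 1.89
- two-sided t-test (noncentral t): 1.59
- four-group ANOVA, group means 0, 0, 0, 2: 1.66
- four-group ANOVA, group means 0, 1, 1, 2: 1.35
- four-group ANOVA, group means 0, 0, 2, 2: 1.91

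The implied SD therefore runs from 1.35 to 1.91.

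**Step 3: worst-case illustration.** Assumptions: two groups of 11 standard normal values, no true difference, two-sided t-test at 5%, 40,000 simulated trials. The number rejected is assumed and does not come from the documents.

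| Rejection pattern | Shift in difference (SD) | Type I error |
|---|---|---|
| None | about 0 | 5.0% |
| 1, 2 or 3 of 11 dropped from one group, unrelated to value and group | none expected | 4.9%, 4.9%, 5.1% |
| Most unfavourable single value dropped, one group | 0.16 | 7.3% |
| Most unfavourable single value dropped in each group, opposite directions | 0.32 | 14.2% |

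A separate run of 200,000 trials gave 7.5% for one group, and 13.9% with a shift of 0.316 SD for both.

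**Step 4: on the ARI scale.** 0.32 × 1.35 = 0.43 and 0.32 × 1.91 = 0.61. The worst-case shift is thus about 0.4 to 0.6 ARI units, or 0.43/2 = 22% to 0.61/2 = 31% of the 2-unit difference in section 11.2.

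**The case against.** The plan has partial safeguards. Rejections must be counted with reasons, so they cannot be silent. The analysis is supervised, and filenames are coded without names or other identifying detail. All of this stands, and it makes unnoticed selective rejection harder. None of it hides the group from the person deciding.

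The documents also do not say who rejects recordings, or whether rejection is manual or automatic. A reader might infer that the researcher edits the signals and discards them on subjective grounds. Signal editing and subjective judgement are not mentioned. That this researcher makes the rejections is a reasonable inference, since rejection happens during analysis and analysis is this person's task, but it is not stated. If the software applies a fixed rule, the gap narrows to the plan's failure to give that rule.

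A reader might also infer that every group comparison is affected. Demographic, history and medication data in section 8.3 do not depend on signal acceptance and are outside the point.

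The strongest objection concerns size. The 14% requires removal of the most unfavourable extreme from both groups in opposite directions, which amounts to selecting on the outcome. Nothing in the documents suggests that this would happen, and value-independent rejection leaves the error near 5%. The planned analysis is a repeated measures ANOVA across four groups (section 11.1), not a two-group t-test. Section 7.1 treats 11 as the number with complete data, so a fall from 11 to 10 need not occur. This objection stands: the figures show vulnerability and do not predict an error rate.

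**Conclusion.** The point holds for signal-derived outcomes: CBFv change, ARI, percentage rejected and percentage derivable. One researcher who knows the diagnosis recruits, records and analyses, and the plan states neither masking nor prespecified acceptance criteria. The existing safeguards reduce the risk of assessor bias without removing it.

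Its actual size cannot be established from the documents. The worst-case shift of about 0.32 SD (type I error about 14%, or about 7% if only one group is affected) depends on the assumed selection pattern and the two-group t-test. Its conversion to about 0.4 to 0.6 ARI units depends on an SD that the plan does not state. It would be wrong to read these as the trial's expected error rate, or as evidence that recordings will be selectively dropped. This is a worthwhile, inexpensive improvement and not a defect that invalidates the design.

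**What to change.** In sections 15.2 and 15.3, state that:

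- an existing team member re-labels the recordings with random codes that carry no group, initials or date;
- signal acceptance or rejection, derivation of CBFv change and ARI estimation are done on the re-labelled files;
- the decisions and the rejection log are locked before the group key is merged;
- acceptance rules are set beforehand for both the CBFv signal and ARI, and any automatic step is described. For ARI, the coherence of at least 0.5 cited in section 4 is one option. It concerns the relation between BP and CBFv, so it does not serve as a rule for CBFv change, which needs its own;
- rejections are reported by group after unmasking.

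The cost is a little extra work and a short delay before unmasking, with no added staff, visits or equipment. Masking the recording session is not practical because the researcher carries out the assessments. Off-line masking will be partial, since the researcher may recognise a recording from memory or from the task-timing markers that section 8.4 places at each ACE-III question.

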**18. PUBLICATION POLICY**

On all publications, the funding body will be acknowledged, and each author will be required to disclose details of their own involvement/contribution in the study (specific publication).

**20. APPENDIX A: EXPECTED EVENTS NOT SUBJECT TO EXPEDITED REPORTING**

Acute Coronary Syndromes	Myocardial infarction
Agitation	Nausea
Angina	Personality change
Anorexia	Peripheral Vascular Disease
Anxiety	Renal impairment
Constipation	Sedation
Delirium	Seizure
Depression	Sexual dysfunction
Dysphagia	Sleep disturbance
Electrolyte disturbance	Stroke
Fall	Transient ischemic attack
Fatigue	Urinary retention
Gastrointestinal disturbance	Urinary tract infection
Hallucinations	Violent behaviour
Incontinence, faecal	Visual loss
Incontinence, urinary	Vomiting
Infections	Weakness
Institutionalisation / Admission to care home	Weight loss
Intracerebral Haemorrhage	
Loss of ability to function or care for self	

[figure not shown]
[figure not shown]
21. APPENDIX B: ADDENBROOKE'S COGNITIVE EXAMINATION-III

[figure not shown]
[figure not shown]
[figure not shown]
[figure not shown]
ADDENBROOKE'S COGNITIVE EXAMINATION – ACE-III English Version A (2012)																								
Name: Date of Birth: Hospital No. or Address:			Date of testing: ___/___/___ Tester's name: _____ Age at leaving full-time education: _____ Occupation: _____ Handedness: _____																					
ATTENTION																								
➤ Ask: What is the	Day _____	Date _____	Month _____	Year _____	Season _____	Attention [Score 0-5] 																		
➤ Ask: Which	No./Floor _____	Street/Hospital _____	Town _____	County _____	Country _____	Attention [Score 0-5] 																		
ATTENTION																								
➤ Tell: "I'm going to give you three words and I'd like you to repeat them after me: lemon, key and ball." After subject repeats, say "Try to remember them because I'm going to ask you later." ➤ Score only the first trial (repeat 3 times if necessary). ➤ Register number of trials: _____						Attention [Score 0-3] 																		
ATTENTION																								
➤ Ask the subject: "Could you take 7 away from 100? I'd like you to keep taking 7 away from each new number until I tell you to stop." ➤ If subject makes a mistake, do not stop them. Let the subject carry on and check subsequent answers (e.g., 93, 84, 77, 70, 63 – score 4). ➤ Stop after five subtractions (93, 86, 79, 72, 65): _____						Attention [Score 0-5] 																		
MEMORY																								
➤ Ask: "Which 3 words did I ask you to repeat and remember?" _____						Memory [Score 0-3] 																		
FLUENCY																								
➤ Letters Say: "I'm going to give you a letter of the alphabet and I'd like you to generate as many words as you can beginning with that letter, but not names of people or places. For example, if I give you the letter "C", you could give me words like "cat, cry, clock" and so on. But, you can't give me words like Catherine or Canada. Do you understand? Are you ready? You have one minute. The letter I want you to use is the letter "P".						Fluency [Score 0 – 7] 																		
						
 
≥ 18	7	
 
14-17	6	
 
11-13	5	
 
8-10	4	
 
6-7	3	
 
4-5	2	
 
2-3	1	
 
0-1	0	
 
total	correct	
 
	≥ 18	7	14-17	6	11-13	5	8-10	4	6-7	3	4-5	2	2-3	1	0-1	0	total	correct
≥ 18	7																							
14-17	6																							
11-13	5																							
8-10	4																							
6-7	3																							
4-5	2																							
2-3	1																							
0-1	0																							
total	correct																							
➤ Animals Say: "Now can you name as many animals as possible. It can begin with any letter."						Fluency [Score 0 – 7] 																		
						
 
≥ 22	7	
 
17-21	6	
 
14-16	5	
 
11-13	4	
 
9-10	3	
 
7-8	2	
 
5-6	1	
 
<5	0	
 
total	correct	
 
	≥ 22	7	17-21	6	14-16	5	11-13	4	9-10	3	7-8	2	5-6	1	<5	0	total	correct
≥ 22	7																							
17-21	6																							
14-16	5																							
11-13	4																							
9-10	3																							
7-8	2																							
5-6	1																							
<5	0																							
total	correct																							

[figure not shown]
MEMORY				

➤ Tell: "I'm going to give you a name and address and I'd like you to repeat the name and address after me. So you have a chance to learn, we'll be doing that 3 times. I'll ask you the name and address later."
 
Score only the third trial.
				
Memory [Score 0 – 7]
 
	1st Trial	2nd Trial	3rd Trial	

Harry Barnes 73 Orchard Close Kingsbridge Devon
	
_____
 
_____
 
_____
	
_____
 
_____
 
_____
	
_____
 
_____
 
_____
	
MEMORY				

➤ Name of the current Prime Minister.....
 
➤ Name of the woman who was Prime Minister .....
 
➤ Name of the USA president.....
 
➤ Name of the USA president who was assassinated in the 1960s.....
				
Memory [Score 0 – 4]
 
LANGUAGE				

➤ Place a pencil and a piece of paper in front of the subject. As a practice trial, ask the subject to "Pick up the pencil and then the paper." If incorrect, score 0 and do not continue further.
 
➤ If the subject is correct on the practice trial, continue with the following three commands below.
 
 
• Ask the subject to "Place the paper on top of the pencil"
 
• Ask the subject to "Pick up the pencil but not the paper"
 
• Ask the subject to "Pass me the pencil after touching the paper"
 
 
Note: Place the pencil and paper in front of the subject before each command.
				
Language [Score 0-3]
 
LANGUAGE				

➤ Ask the subject to write two (or more) complete sentences about his/her last holiday/weekend/Christmas. Write in complete sentences and do not use abbreviations. Give 1 point if there are two (or more) complete sentences about the one topic; and give another 1 point if grammar and spelling are correct.
				
Language [Score 0-2]
 
LANGUAGE				

➤ Ask the subject to repeat: 'caterpillar'; 'eccentricity'; 'unintelligible'; 'statistician' Score 2 if all are correct; score 1 if 3 are correct; and score 0 if 2 or less are correct.
				
Language [Score 0-2]
 

LANGUAGE	

➤ Ask the subject to repeat: 'All that glitters is not gold'
	
Language [Score 0-1]
 

➤ Ask the subject to repeat: 'A stitch in time saves nine'
	
Language [Score 0-1]
 
LANGUAGE	

➤ Ask the subject to name the following pictures:
 
 
 
_____ 
  
 
 
_____ 
  
 
 
_____ 
  
 
 
_____ 
  
 
 
_____ 
  
 
 
_____ 
  
 
 
_____ 
  
 
 
_____ 
  
 
 
_____ 
  
 
 
_____ 
  
 
 
_____ 
  
 
 
_____ 
  
 
	
Language [Score 0-12]
 
LANGUAGE	

➤ Using the pictures above, ask the subject to:
 
 
• Point to the one which is associated with the monarchy ..... .....
 
• Point to the one which is a marsupial ..... .....
 
• Point to the one which is found in the Antarctic ..... .....
 
• Point to the one which has a nautical connection ..... .....
 
	
Language [Score 0-4]
 

LANGUAGE	

➤ Ask the subject to read the following words: (Score 1 only if all correct)
 
sew pint soot dough height
	
Language [Score 0-1]
 
VISUOSPATIAL ABILITIES	

➤ Infinity Diagram: Ask the subject to copy this diagram
	
Visuospatial [Score 0-1]
 
	

➤ Wire cube: Ask the subject to copy this drawing (for scoring, see instructions guide).
	
Visuospatial [Score 0-2]
 
	

➤ Clock: Ask the subject to draw a clock face with numbers and the hands at ten past five. (For scoring see instruction guide: circle = 1, numbers = 2, hands = 2 if all correct).
	
Visuospatial [Score 0-5]
 

VISUOSPATIAL ABILITIES	

➤ Ask the subject to count the dots without pointing to them
	
Visuospatial [Score 0-4]
 
 	 
 	 

VISUOSPATIAL ABILITIES					
➤ Ask the subject to identify the letters					Visuospatial [Score 0-4] 
					
					
MEMORY					
➤ Ask "Now tell me what you remember about that name and address we were repeating at the beginning"					
Harry Barnes 73 Orchard Close Kingsbridge Devon	..... ..... ..... .....				Memory [Score 0-7] 
MEMORY					
➤ This test should be done if the subject failed to recall one or more items above. If all items were recalled, skip the test and score 5. If only part was recalled start by ticking items recalled in the shadowed column on the right hand side; and then test not recalled items by telling the subject "ok, I'll give you some hints: was the name X, Y or Z?" and so on. Each recognised item scores one point, which is added to the point gained by recalling.					Memory [Score 0-5] 
Jerry Barnes 37	Harry Barnes 73	Harry Bradford 76		recalled	
Orchard Place Oakhampton	Oak Close Kingsbridge	Orchard Close Dartington		recalled	
Devon	Dorset	Somerset		recalled	
SCORES					
				TOTAL ACE-III SCORE	/100
				Attention	/18
				Memory	/26
				Fluency	/14
				Language	/26
				Visuospatial	/16

